**26.10.3. Eyelash (length and Density) Assessment**  
Eyelash length will be measured with the eyelid closed and the subject's head positioned to show the full length of the lashes.

[REDACTED]

Eyelash density will be evaluated

[REDACTED]

**26.10.4. Periorbital Assessment**  
The distance from

[REDACTED]

**26.10.5. Blood Sampling**  
Blood sampling will be performed to evaluate systemic drug concentrations of the travoprost acid in subjects' plasma. As noted in Section 7.3 and Appendix A, at the

**CLINICAL PROTOCOL**

Date: September 16, 2016	Phase: Phase II Study	Protocol No.: GC-009
-----------------------------	--------------------------	-------------------------

baseline, Week 1-2 (10 day  $\pm$  3), Week 12 and Month 12 examinations, blood samples will be obtained from each study subject at a lab in close proximity to the investigational site.

## List of Abbreviations

AE	Adverse Event
ANCOVA	Analysis of Covariance
BSCVA	Best Spectacle Corrected Visual Acuity
C/D	Cup-to-Disc
CI	Confidence Interval
COV	Coefficient of Variation
CRF	Case Report Form
CS	Compound Symmetry
dB	Decibels
ECD	Endothelial Cell Density
ETDRS	Early Treatment of Diabetic Retinopathy Study
ICE	Intercurrent Events
IOP	Intraocular Pressure
ITT	Intent-To-Treat
LogMAR	Logarithm of the Minimum Angle of Resolution
MAR	Missing At Random
MedDRA	Medical Dictionary for Regulatory Activities
MI	Multiple Imputation
MCMC	Monte Carlo Markov Chain
MNAR	Missing Not At Random
mmHg	Millimeters of Mercury
MMRM	Mixed Model for Repeated Measures
NRI	Non-Responder Imputation
OAG	Open-Angle Glaucoma
OC	Observed Case

OHT	Ocular Hypertension
PP	Per-Protocol Analysis set
PT	Preferred Term
SAE	Serious Adverse Event
SOC	System Organ Class
TEAE	Treatment Emergent Adverse Event
TOEPLH	Toeplitz
UN	Unstructured
VF	Visual Field

## Version History

This Statistical Analysis Plan (SAP) for GC-009 is based on the protocol dated on 16SEP2016.

## 1. Introduction

This Phase 2 study evaluates the safety and efficacy of two intraocular implants that elute travoprost at different rates in subjects with open-angle glaucoma (OAG) or ocular hypertension (OHT). The study duration is 36 months postoperative. One database lock will occur after all subjects have either completed the Month 36 visit or discontinued prematurely.

An analysis will be conducted after all subjects either completed the Month 3 visit or have discontinued prematurely prior to Month 3. At that time, the randomization code will be unmasked to the project team after all the data queries related to the efficacy and safety outcomes are resolved and corresponding data revisions are completed in the database.

This statistical analysis plan provides details of the planned analyses to be performed at the time of the Month 36 database lock. Shells of tables, listings and figures are presented in a separate document.

[figure not shown]
This document is based on Protocol Amendment 2 (16 September 2016). The statistical definitions and analytical methods described in this SAP supersede that in the protocol. Any revisions to the primary endpoint analyses and significant revisions to the secondary endpoint analyses will be made prior to the database lock. Reasons for such revisions will be described in the final Clinical Study Report (CSR).

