9.1. Power Calculation and Determination of Sample Size

9.2. Statistical Hypotheses and Level of Significance

9.3. Unmasking of Randomization

**CLINICAL PROTOCOL**

Date: September 16, 2016	Phase: Phase II Study	Protocol No.: GC-009
-----------------------------	--------------------------	-------------------------

[REDACTED] For the

final analyses, when all subjects have completed the 12-week Visit, the randomization code will be unmasked to the project team after all the data queries related to the efficacy and safety outcomes have been resolved and corresponding data revisions have been completed in the database.

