**9.5.4.3. Per Protocol Population (PP)**

The Per Protocol Population is a subset of ITT. It includes all the ITT subjects who received the treatment and medication drops based on the randomization schedule and do not have the major protocol deviations. The major protocol deviations will be determined with the study Medical Monitor in a mask fashion prior to the database lock for the final analyses for the 12-week data. The PP population will be used in the sensitivity analysis for the mean IOP comparisons.

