**16.2. Data Collection**

The clinical investigator must maintain detailed records on all enrolled subjects. Data for enrolled subjects will be collected with an electronic data capture system. The electronic database, which is Title 21 CFR Part 11 compliant, will be managed by a data management vendor. Access to the database will be granted to authorize study personnel based on their role after training; and the access will be password-protected. The data clarification process will be managed within the electronic data capture system by either system-generated or manually generated electronic queries. Accuracy of data will be verified by 100% source data verification at regular intervals, and all corrections to data will be made in the database.

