## 6. Efficacy Analyses

### 6.1. Primary Efficacy Endpoints Analysis

#### 6.1.1. Definition of Endpoints

The primary efficacy measure in this study is IOP. Diurnal IOP (measured at 8AM, 10AM, and 4PM) is evaluated at Baseline, Day 10, Week 6, and Month 3. Standard IOP (measured at 8AM) is evaluated at Week 4 and Months 6, 9, 12, 15, 18, 21, 24, 27, 30, 33, and 36. [REDACTED]

The primary efficacy endpoint is the diurnal IOP in the study eye at 8AM, 10AM, and 4PM at each of Day 10, Week 6, and Month 3 visits (9 timepoints).

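### The SAP has one database lock, after Month 36, while the protocol assumes a lock for the 12-week data; nothing visible fixes the primary data, the per-protocol decisions or the primary analysis before the project team is unmasked at Month 3

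*SAP*

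**What the plan says.** **Lock.** SAP 1 (Introduction): "One database lock will occur after all subjects have either completed the Month 36 visit or discontinued prematurely". The same section says that the SAP covers the analyses to be run at that Month 36 lock. These include the primary IOP analysis in SAP 6.1.5.

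**Month 3 analysis and unmasking.** SAP 1 continues: "An analysis will be conducted after all subjects either completed the Month 3 visit or have discontinued prematurely prior to Month 3". The code goes to the project team at that point, on condition that open queries on efficacy and safety "are resolved and corresponding data revisions are completed in the database". Protocol 9.3 has the same step for its final analyses: "when all subjects have completed the 12-week Visit, the randomization code will be unmasked to the project team", again once queries and revisions are finished.

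**The protocol's 12-week lock.** Protocol 9.5.4.3 has major deviations settled with the Medical Monitor under masking, "prior to the database lock for the final analyses for the 12-week data".

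**Decisions tied to the lock in the SAP.** SAP 5.2 leaves the sorting of deviations into major and minor to the study team, with database lock as the deadline; its visible text does not mention masking. Subjects with major deviations drop out of the per-protocol set, which Sensitivity Analysis 1 (SAP 6.1.6) uses. SAP 1 also sets database lock as the deadline for revising the primary endpoint analyses.

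**Data corrections.** Protocol 16.2 provides full source verification at intervals and says that "all corrections to data will be made in the database". It gives no end date for this.

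**The concern.** All nine primary readings per subject are collected by Month 3. The ordinary safeguard is to fix those data, and every decision that shapes the primary result, before anyone on the team sees the treatment code. The protocol supplies this through its 12-week lock. The SAP's single-lock statement removes it and puts only a cleaning condition in its place.

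Three things depend on this:

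- **The data values.** Without a stated lock or freeze, a reader of the final report cannot confirm that the Day 10, Week 6 and Month 3 readings analysed at Month 36 are the ones that existed when the code was released.
- **The per-protocol set.** The protocol has the deviation decision made masked and before the 12-week lock. The SAP lets it wait for the Month 36 lock, when the study team may already know the arms.
- **The primary analysis.** SAP 1 permits revisions to it up to the lock, and therefore after unmasking.

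The second and third follow most directly from the text, because the SAP itself names database lock as their deadline. A further loose end is that the same nine timepoints may be reported at Month 3 and again at Month 36. The SAP does not say which result is primary.

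**Working it through.** The documents give no figure for the time between unmasking and lock, so there is none to reproduce. The check sets the passages in order and then works out the interval from the visit schedule.

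**Sequence of events**

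| Step | Protocol | SAP |
|---|---|---|
| Condition for code release | Queries and revisions finished (9.3) | Same (1) |
| Code released to the project team | At 12 weeks (9.3) | At Month 3 (1) |
| Lock of the 12-week data | Assumed (9.5.4.3) | None visible; one lock, after Month 36 (1) |
| Major deviations decided | Masked, before the 12-week lock (9.5.4.3) | By the study team, before database lock (5.2) |
| Primary analysis run | Once all subjects could have had the 12-week visit (9.6.1) | Among the analyses at the Month 36 lock (1, 6.1.5) |
| Deadline for revising the primary analysis | Not seen in the visible text | Before database lock (1) |

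Unmasking comes at the same point in both documents. The lock does not, and in the SAP the last three rows follow the lock.

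**Does the SAP's precedence clause settle it?** SAP 1 says the SAP prevails over the protocol for statistical definitions and analytical methods. A database lock is neither, so the clause does not clearly resolve the conflict.

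**Interval from unmasking to the SAP's lock**

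Inputs, from protocol 4.1: Week 12 visit at day 91 ± 7; Month 36 visit at day 1095 ± 60.

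Formula: gap = Month 36 day − Week 12 day, for the subject who reaches both visits last, with 1 month = 365.25 / 12 = 30.44 days.

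- Nominal: 1095 − 91 = 1,004 days; 1,004 / 30.44 = 33.0 months.
- Shortest: (1095 − 60) − (91 + 7) = 1035 − 98 = 937 days = 30.8 months.
- Longest: (1095 + 60) − (91 − 7) = 1155 − 84 = 1,071 days = 35.2 months.

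Time spent resolving queries before unmasking shortens the interval, and cleaning before the final lock lengthens it. Neither duration is given, so 33 months is a nominal figure and not a ceiling.

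**Number of readings concerned.** About 150 subjects × 9 timepoints = 1,350 planned readings. This is the most that could be involved, not a count of readings expected to change.

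**With a lock or freeze before code release,** the interval in which the Month 3 data are unlocked after unmasking is 0 months.

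**The case against.** A reader might infer that the primary readings remain open to editing for 33 months and would be corrected by people who know the arm. The documents do not support that:

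- Both documents require revisions arising from efficacy and safety queries to be finished before the code is released. Protocol 16.2 does not say that Month 3 readings are reopened afterwards.
- The code goes to the project team. Protocol 4.1 and 11 keep subjects, and the staff who perform certain measures, masked throughout. The documents do not say whether anyone on the project team can raise queries or change data.
- Protocol 16.2 describes a Part 11 compliant system with role-based access and query-managed clarification. These controls make a change easier to trace.
- Text just before the unmasking sentence in protocol 9.3 is redacted, the body of 9.4.2 and 9.4.3 is not visible, and part of the SAP's per-protocol definition is blacked out. A freeze or a masking rule could be stated there or in a data-management document.

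A reader might also infer that nothing says which result is primary. Protocol 9.6.1 places the primary analysis after the 12-week visit, and 9.3 calls the 12-week analyses final, so the protocol does speak to this. The SAP's Month 36 scope is what needs reconciling with it.

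Finally, SAP 2.2 says that no formal efficacy hypotheses were specified, which lowers the stakes, although the estimand in SAP 2.1 refers to non-inferiority.

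These points stand, and they limit the finding to an absent control; they show no open data and no biased result. They do not remove the conflict. Cleaning is not a lock, the SAP says there is one lock, and the protocol relies on an earlier one.

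**Conclusion.** The concern holds as a conflict between the documents that displaces a protocol safeguard. As the SAP is written, the nine primary timepoints are not shown to be fixed before unmasking. The deviation classification and revisions to the primary analysis need only precede a lock that falls nominally 33 months after the Month 3 visit (30.8 to 35.2 months with the visit windows).

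This rests on two assumptions: that no redacted or separate text states a Month 3 freeze, and that the same last subject determines both the Month 3 analysis and the final lock. If a freeze is stated elsewhere, the remedy shrinks to citing it. The interval would change if the last subject left early.

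No effect on the treatment difference can be calculated, because the documents give no basis for how many readings might change or by how much. Nothing here suggests that any improper change is intended. The point should be corrected because the remedy is specific and cheap and protects the primary result.

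**What to change.** 1. In SAP 1, state that data through the Month 3 visit are locked, or frozen and archived with an audit trail, before the code is released, consistent with protocol 9.5.4.3. If such a step is already documented elsewhere, cite it.
2. In SAP 5.2, require the major/minor deviation decisions that define the per-protocol set to be made masked and before that point.
3. In SAP 1, make the same point the deadline for revisions to the primary analysis.
4. State that the primary result is the one from this dataset, as protocol 9.6.1 implies.
5. Log any later correction to these readings with its date and reason, and show its effect on the primary result at Month 36. A reading later found wrong against source is then visibly corrected, while the primary result still comes from data fixed before unmasking.

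The cost is one extra data cut, a change log and one repeated table, plus the SAP wording. No visit or assessment changes.

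### SAP section 1 lets the primary IOP analyses be revised until a lock after Month 36, although the project team is unmasked at Month 3, when data collection for all 9 primary timepoints has ended

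*SAP*

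**What the plan says.** Most of the relevant text is in SAP section 1.

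- **Locks.** "One database lock will occur after all subjects have either completed the Month 36 visit or discontinued prematurely". No other lock is dated in the visible SAP. The section adds that this SAP covers the "planned analyses to be performed at the time of the Month 36 database lock".
- **Unmasking.** An analysis takes place once every subject has passed Month 3 or left the study. "At that time, the randomization code will be unmasked to the project team", after query resolution. Protocol 9.3 has the same timing: for the "final analyses, when all subjects have completed the 12-week Visit, the randomization code will be unmasked to the project team".
- **Revisions.** "Any revisions to the primary endpoint analyses and significant revisions to the secondary endpoint analyses will be made prior to the database lock". The reasons for any revision are to be given in the final study report.
- **Precedence.** "The statistical definitions and analytical methods described in this SAP supersede that in the protocol".

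SAP 2.1 and 6.1.1 define the primary endpoint as study-eye IOP at 8 AM, 10 AM and 4 PM on Day 10, at Week 6 and at Month 3. Protocol 9.6.1 places the primary analysis after the 12-week visit. Protocol 9.5.4.3 refers to a database lock for the 12-week data, as the point before which major deviations are judged masked for the per-protocol set.

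**The concern.** Prespecification protects an estimate only if the method is fixed before anyone who can change it sees results by treatment. Here the deadline for changing the primary analysis is tied to a lock that falls after unmasking. The visible text neither limits revisions to the time before unmasking nor assigns them to staff who remain masked. An explanation in the study report tells the reader that a change was made, but it does not prevent a choice informed by the results.

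What is at stake is the credibility of the primary mean IOP differences. SAP 2.2 says that no formal efficacy hypotheses were specified. Even so, the estimand in SAP 2.1 presents these differences as the basis for judging non-inferiority to timolol, and protocol 9.6.4.1 attaches 95% confidence intervals to them.

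**Working it through.** **1. What is complete at unmasking.** Inputs are from SAP 6.1.1: 3 clock times and 3 visits.

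- Primary timepoints: 3 × 3 = 9, which reproduces the SAP's own count.
- Implant-versus-timolol comparisons: 9 × 2 implants = 18.
- Latest primary visit: Month 3. At the Month 3 analysis, collection has therefore ended for 9 of 9 timepoints and 18 of 18 comparisons. Ended means that no further primary data are due. Some values may still be missing.

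**2. Order of events.**

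| Event | Timing | Source |
|---|---|---|
| Last primary timepoint | Month 3 visit (nominal day 91) | SAP 6.1.1; protocol 4.1 |
| Project team unmasked | Month 3 analysis, after queries | SAP 1; protocol 9.3 |
| Only lock named in the visible SAP | After Month 36 (nominal day 1095) | SAP 1; protocol 4.1 |
| Primary-analysis revisions close | Before the lock | SAP 1 |

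For one subject the two visits are nominally 1095 − 91 = 1004 days apart. This shows only that the two events are far apart. It does not measure bias, and the interval for the whole study depends on accrual dates that the documents do not give.

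**3. Which lock closes revisions?** The visible text offers two candidates.

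- *The lock after Month 36.* This is the plain reading. SAP section 1 names one lock and then refers to the lock in the singular. Revisions then stay open after unmasking.
- *The 12-week lock in protocol 9.5.4.3.* This could close revisions before unmasking. But the SAP says there is one lock, at Month 36, and that its own definitions and methods take precedence. The protocol uses the 12-week lock only to time the masked decision on deviations. Nothing in the SAP ties the revision deadline to it.

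**4. Any other safeguard?** SAP section 9 says that no interim analysis is planned and sets no rule for the Month 3 analysis. The only control in visible text is the explanation in the study report.

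**The case against.** The strongest reply is about scope. This SAP says that it serves the Month 36 lock. The protocol places the primary analysis at 12 weeks, calls those analyses final and refers to a lock for the 12-week data. On that view the primary result came out at Month 3 under the protocol or a separate plan, and the revision clause concerns only later re-reporting. A Month 3 rule may also sit in text that is not visible: the missing figure in SAP section 1, blacked-out parts of SAP sections 3, 6.1.5 and 6.1.7, SAP section 10, or protocol 9.3.

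Part of this stands. An unseen rule is possible, and it limits confidence. But this SAP restates the primary endpoint and primary analysis, claims precedence over the protocol and leaves both open to revision until the lock. If another plan governed Month 3, the SAP should name it.

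A reader might go further and infer that the primary method was changed after unmasking. Protocol 9.6.4.1 derives least-squares means and 9.6.4.4 refers to a repeated-measures model, whereas SAP 6.1.6 describes the primary analysis as a t-test. The documents do not support that inference:

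- The model text in protocol 9.6.4.1 and SAP 6.1.5 is largely blacked out, and the repeated-measures wording is visible only for subgroups.
- The SAP abbreviation list includes MMRM, ANCOVA and three covariance structures (unstructured, compound symmetry, Toeplitz), so a repeated-measures analysis may be in hidden text.
- The SAP's date is not visible, so any change cannot be placed before or after unmasking.

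The apparent difference is a reason to document timing and nothing more. Nor can a loss of type I error control be claimed, because no formal efficacy hypotheses are specified.

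**Conclusion.** The clause is wrong as written, at minor severity. It permits the primary analysis to be revised when treatment-coded primary results are available. It reaches all 9 timepoints and all 18 comparisons. The size of any resulting bias cannot be computed from the documents, and no revision after unmasking is shown.

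The conclusion assumes that the lock in the revision clause is the single lock named in the same section, and that no hidden text sets a tighter deadline. Because the second assumption cannot be checked, confidence is moderate. A reader might also infer from SAP 5.2, which does not mention masking, that deviations may be classified unmasked. That does not follow, since protocol 9.5.4.3 requires masked classification and SAP 5.2 does not contradict it.

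**What to change.** 1. In SAP section 1, make the cut-off for revising analyses of the nine primary timepoints the time before unmasking for the Month 3 analysis. Label any later change post hoc and report it beside the analysis in force at unmasking.
2. If unmasking preceded this SAP, name the analysis that was in force at unmasking, whether from the protocol or a separate plan, and keep it as primary. Where this SAP's analysis differs, report it beside the primary one as post hoc. Record the dates of unmasking and of this SAP so that the order is clear.
3. Reconcile the single lock in SAP section 1 with the 12-week lock in protocol 9.5.4.3, and say which one each deadline refers to.

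The cost is a few sentences in SAP section 1. If unmasking has already happened, it may also mean presenting two versions of the primary analysis. No new data, subjects or visits are needed.

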### Protocol and Amendment History

Version	Approval Date
Original Protocol	14 November 2015
Amendment 1	08 July 2016
Amendment 2	16 September 2016

## 2. Objectives and Study Design

### 2.1. Objectives, Endpoints, and Estimands

Objectives	Endpoints
Efficacy	
To compare the efficacy of intraocular implants containing travoprost at two different elution rates versus Timolol Maleate Ophthalmic Solution, USP, 0.5% (timolol) in reducing elevated intraocular pressure in subjects with open-angle glaucoma (OAG) or ocular hypertension (OHT)	
Primary Efficacy Endpoint:
 

• The primary efficacy endpoint is the diurnal IOP in the study eye at 8AM, 10AM, and 4PM at each of Day 10, Week 6, and Month 3 visits (9 timepoints).

 

	
Safety	
To compare the safety of intraocular implants containing travoprost at two different elution rates versus Timolol Maleate Ophthalmic Solution, USP, 0.5% (timolol) in reducing elevated intraocular pressure in subjects with open-angle glaucoma (OAG) or ocular hypertension (OHT)
 

• Adverse events

• Surgical complications

• Best spectacle-corrected visual acuity

• Slit-lamp examination findings

• Gonioscopy findings

• Ophthalmoscopy findings

• Pachymetry

• Visual field evaluation

• Endothelial cell assessment

• Conjunctival hyperemia

• Periorbital assessment

• Iris assessment (color)

• Eyelash assessments (density, length)

• Blood laboratory testing of human plasma (systemic exposure to travoprost free acid)

Estimand: the four attributes of the estimand are defined as the following:

1. Population: ITT population including all randomized subjects. Subjects with open-angle glaucoma or ocular hypertension defined through enrollment criteria. [REDACTED]
2. Variable (endpoint): Post-baseline IOP at 8AM, 10AM and 4PM at each of Day 10, Week 6, and Month 3 visits (9 timepoints). [REDACTED]
3. [REDACTED]
4. Population-level summary parameter: difference in post-baseline IOP means between treatment groups for evaluating of non-inferiority.

